5.3 Treatment assignment

Patients will continue receiving study treatment as per their treatment arm in the core studies (i.e., CAIN457A2304 or CAIN457A2307) until Week 156. The randomization numbers will be generated using the following procedure to ensure that treatment assignment is concealed from patients and investigator staff. A randomization list will be produced by or under the responsibility of Novartis Drug Supply Management using a validated system that automates the random assignment of treatment arms to randomization numbers in the specified ratio.

At the end of Week 52 of CAIN457A2304 (or Week 40 of CAIN457A2307), the investigator will complete core study assessments, enter the PASI response into the eCRF and register the completion of core study visit in the IRT. The Week 52 of CAIN457A2304 (or Week 40 of CAIN457A2307) visit in the core study is the randomization visit for CAIN457A2304E1. Based on the fulfillment of inclusion/exclusion criteria by the subject and IRT notification from the database of core studies at Week 52 (explained above), the investigator (or designee) will call the IRT set up of CAIN457A2304E1. The randomization number will be adopted from core study (CAIN457A2304 and CAIN457A2307) in this extension study and IRT will only specify a unique medication number for the first package of investigational treatment to be dispensed to the patient. The randomization number will not be communicated to the caller and the treatment assignment will be unbiased and concealed from patients and investigator staff.

The randomization list from the core study CAIN457A2304 or CAIN457A2307 will be adopted for this extension study. A separate medication list will be produced by or under the responsibility of Novartis Drug Supply Management using a validated system that automates the random assignment of medication numbers to packs containing the investigational drug(s).

At Week 156, all subjects will be unblinded and will continue with one of the treatment options described in [Section 5.2](#) based on their previous treatment arm and the investigator's judgment. The investigator should select the best option from the options based on the assigned treatment up to that point. This selection should be based on knowledge of and experience with the patient.

5.4 Treatment blinding

Subjects, investigator staff and persons performing the assessments will remain blind to the identity of the treatment, for subjects who participated in the core CAIN457A2304 study, from the time of enrollment in the extension study until Week 156, using the following methods:

- (1) Randomization data from the core study are kept strictly confidential until the time of unblinding, and will not be accessible by anyone else involved in the study
- (2) The identity of the treatments will be concealed by the use of investigational treatments that are identical in packaging, schedule of administration and appearance. Unblinding will only occur in the case of subject emergencies (see [Section 5.5.11](#)).

In order to maintain the blind for the subjects coming from study CAIN457A2304, placebo PFSSs are used.

Subjects participating from the CAIN457A2307 core study, as well as investigator staff, persons performing the assessments and data analysts will be unblinded to the treatment that these subjects are receiving throughout the duration of this extension study.

In addition, the bioanalyst will have access to the randomization lists from the core study to facilitate analysis of pharmacokinetic samples. The bioanalyst will keep the information confidential.

5.5 Treating the patient

5.5.1 Patient numbering

Each patient is uniquely identified by a Subject Number which is composed by the site number assigned by Novartis and a sequential number assigned by the investigator. Once assigned to a patient, the Subject Number will not be reused. The Subject Number is maintained from the core study/ studies in the extension.

Upon signing the informed consent form, the investigator or his/her staff will contact the IRT and provide the requested identifying information for the patient to register them into the IRT. The site should select the CRF book with a matching Subject Number from the EDC system to enter data.

If the patient fails to be treated for any reason, the IRT must be notified within two days that the patient was not treated. The reason for not being treated will be entered on the Screening Epoch Study Disposition CRF.

5.5.2 Dispensing the investigational treatment

Each study site will be supplied by Novartis with investigational treatment in packaging of identical appearance.

The investigational treatment packaging has a two-part label. A unique randomization number is printed on each part of this label which corresponds to one of the 5 treatment arms and a specific visit. Investigator staff will identify the investigational treatment package(s) to dispense to the patient by contacting the IRT and obtaining the medication number(s). Immediately before dispensing the package to the patient, investigator staff will detach the outer part of the label from the packaging and affix it to the source document (Drug Label Form) for that patient's unique subject number.

5.5.3 Handling of study treatment

5.5.3.1 Handling of investigational treatment

Investigational treatment must be received by a designated person at the study site, handled and stored safely and properly, and kept in a secured location to which only the investigator and designees have access. Upon receipt, all investigational treatment should be stored according to the instructions specified on the labels. Clinical supplies are to be dispensed only in accordance with the protocol.

Medication labels will be in the local language and comply with the legal requirements of each country. They will include storage conditions for the investigational treatment but no

information about the patient except for the medication number. The investigator must maintain an accurate record of the shipment and dispensing of investigational treatment in a drug accountability log. Monitoring of drug accountability will be performed by the field monitor during site visits and at the completion of the trial. At the conclusion of the study, and as appropriate during the course of the study, the investigator will return all unused investigational treatment, packaging, drug labels, and a copy of the completed drug accountability log to the Novartis monitor or to the Novartis address provided in the investigator folder at each site.

Handling of other study treatment

Not applicable.

5.5.4 Instructions for prescribing and taking study treatment

Prefilled syringes are packaged as one syringe per box. Until Week 156, each subject will require two boxes of PFSs per dose.

- One secukinumab 150 mg PFS and one placebo secukinumab PFS (150 mg dose) OR
- Two secukinumab 150 mg PFS (300 mg dose) OR
- Two placebo secukinumab 150 mg PFS (Placebo dose for subjects in the SoR regimen, who have not relapsed)

After Week 156, subjects with site visits every 12-16 weeks will be expected to perform home administrations at the protocol specified time points (every 4 weeks) when there is no correlated office visit. In these cases, the investigator will dispense, via IRT, the appropriate number of investigational treatment packages for the planned home administrations until the next expected site visit and detach the outer part of the label from the packaging prior to giving the package to the subject. The subjects will record the date(s) of administration at home and will return the used medication and packaging at their next site visit. Subjects will be asked to return all unused medication and packaging at the latest by the completion of the study or discontinuation of investigational treatment. Site staff will record the dates of administration on the appropriate documents.

All study treatment kits assigned to the subject during the study will be recorded / databased in the IRT.

The syringes with the ready-to-use study treatment solution (PFS) will be provided by the site staff during the study visit.

The first study treatment administration will occur at Week 52 (enrollment into the extension) after all study scheduled assessments have been performed (and inclusion / exclusion criteria confirmed) and only after the scheduled blood samples have been drawn. It is preferred that the subject self-inject the treatment during the site visit, however, if a subject is not able or not willing to self-administer, administration will be performed by study site staff. If the subject is not able or not willing to self-administer the PFS at home, he/she may come into the site for dosing every 4 weeks.

For subjects willing to self-inject, the first use at enrollment visit (Week 52) will take place under guidance and the supervision of one site staff member. At the enrollment visit (Week 52) the site staff will walk subjects through the “Instructions For Use” on how to self-inject via PFS. At the following visits, subjects will receive the PFS and instructions at the study site to follow on their own.

NOTE: The needle cover of the syringe contains dry rubber (latex), which should not be handled by persons sensitive to this substance.

During the treatment period from Week 52 until Week 256, subjects will receive a maximum of 104 study treatment injections (2 injections of secukinumab 150 mg PFS and/or placebo PFS at each visit). The actual number of study treatment injections will depend on the treatment assigned. All subjects will receive 52 study treatment injections between Week 52 and Week 152 (2 injections of secukinumab 150 mg PFS and/or placebo PFS at each visit); between Week 156 and 256 subjects could receive as many as 52 study treatment injections (2 injections of secukinumab 150 mg PFS every four weeks) or as few as 0 study treatment injections (SoR treated subjects who do not meet start of relapse criteria at any point).

At study visits when pre-dose blood samples have to be drawn ([Table 6-1](#)), the study treatment will be injected to the subject only after the blood samples have been taken.

At each visit, all study assessments, including the completion of Patient Reported Outcomes (PROs), should be completed prior to the self injection of study treatment.

After Week 256, no further study treatment will be administered during the treatment period. In addition, no study treatment is administered during the follow-up period and follow-up 2 period.

The subject should be instructed to contact the investigator if he/she is unable for any reason to attend a study visit as scheduled.

All dates, times of injections, mode of injection (self or by study site staff) during the study must be recorded on the Dosage Administration Record eCRF. Immediately before dispensing the package for injection, investigator staff will detach the outer part of the label from the packaging and affix it to the source document (Drug Label Form) for that subject's unique subject number.

The investigator should promote compliance by instructing the subject to attend the study visits as scheduled and by stating that compliance is necessary for the subject's safety and the validity of the study.

Administration

Secukinumab solution for s.c. injection or placebo secukinumab solution (active or placebo, respectively) will be provided in a PFS.

The study treatment solution must be injected in non-affected areas of the skin. If possible, throughout the trial administer the study treatment to one of the following body regions, changing the injection site from visit to visit: right thigh, left thigh, right stomach, left stomach, upper outer arm (when assisted by attendant).

Prior to administration the boxes containing the PFS with study treatment solution should be allowed to come to room temperature unopened for about 20 minutes before administration. Used PFS should be disposed immediately after use in a sharps container OR according to the regulatory needs of the respective countries.

Home administration

After Week 156 (two years of self-administered study treatment under the supervision of site staff), subjects will be expected to self-administer the PFS at home when they are not visiting the site for any other trial related procedure. Subjects must be instructed to contact the investigator/site staff prior to any self-administration if they have any AEs or SAEs to report. The subjects will be allowed to self-administer treatment at home only if they have exhibited correct self-administration of the PFS at the site. If the subject is not able or not willing to self-administer the PFS, he or she should visit the site every 4 weeks, according to the visit schedule, and the staff or subject will administer the study drug at the site. However, during those visits no other assessments will be performed other than checking vitals (recorded in source) and checking for AEs or SAEs.

5.5.5 Permitted dose adjustments and interruptions of study treatment

Other than the protocol-specified dosing-changes at Week 156, no dose adjustments or interruptions are permitted.

A positive urine pregnancy test during the treatment periods of the study requires immediate interruption of study treatment until serum β -hCG is performed and found to be negative. If the serum β -hCG test is positive, the subject must be discontinued from the trial.

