Study drug/ treatment	Any single drug or combination of drugs administered to the patient as part of the required study procedures; includes investigational drug (s), active drug run-ins or background therapy
Study/investigational treatment discontinuation	Point/time when patient permanently stops taking study/investigational treatment for any reason; may or may not also be the point/time of premature patient withdrawal
Variable	Information used in the data analysis; derived directly or indirectly from data collected using specified assessments at specified time points

Amendment 2

Amendment rationale

FDA has requested the following post marketing commitment be applied to this study: *"Complete the treatment and evaluation of subjects enrolled in the ongoing CAIN457A2304E1 trial for a duration of 4 years, unless a safety signal is identified that indicates the potential risks of such continued long-term treatment outweigh the benefits. Evaluation of subjects should continue through the end of the trial when achievable (even if treatment is not continued for the duration). Subjects will be followed for the occurrence of serious infection, tuberculosis, opportunistic infections, malignancy, hypersensitivity reactions, autoimmune disease, neurologic or demyelinating disease, cardiovascular, gastrointestinal or hematologic adverse events".*

Subjects who complete treatment period and follow-up period are evaluated for 4 years regarding respective adverse events. However, patient who prematurely discontinue treatment are evaluated for less than 4 years.

Therefore, this amendment extends the evaluation of subjects who prematurely discontinue treatment regarding respective adverse events and concomitant medications in order to achieve a 4 year evaluation period. Evaluation of subjects should continue when achievable even if treatment is not continued for the duration. All subjects who prematurely discontinue treatment should complete all assessment of Week 260 (end of treatment visit) and of the follow-up period visits (Weeks 264 and 268). Subsequently, adverse events and use of concomitant medication will be evaluated by the investigator through telephone calls every 3 months for a duration of 4 years from the time when subject has been enrolled into CAIN457A2304E1 study. If deemed necessary by the investigator unplanned assessments at site might be scheduled during this time.

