5.5.9 Discontinuation of study treatment and premature patient withdrawal

Subjects may voluntarily withdraw from the study for any reason at any time. They may be considered withdrawn if they state an intention to withdraw, fail to return for visits, or become lost to follow-up for any other reason.

Discontinuation from a treatment period

If premature withdrawal occurs for any reason, the investigator must make every effort to determine the primary reason for a subject's premature withdrawal from the study and record this information on the end of treatment (EOT) eCRF (Week 260).

Study treatment *must* be discontinued under the following circumstances:

- Withdrawal of informed consent
- Emergence of the following adverse events: adverse events that in the judgment of the investigator, taking into account the subject's overall status, prevent the subject from continuing participation in the study (for example, sepsis or serious infection).
- Any laboratory abnormalities that in the judgment of the investigator, taking into consideration the subject's overall status, prevents the subject from continuing participation in the study.
- Pregnancy (see [Section 6.5.6](#) and [Section 7.4](#))
- Continued use of prohibited treatment as per recommendations in [Table 5-4](#).
- Any other protocol deviation that results in a significant risk to the subject's safety

In addition to the requirements mentioned above for study treatment discontinuation, the investigator should discontinue study treatment for a given subject if, on balance, he/she believes that continuation would be detrimental to the subject's well-being.

Subjects who discontinue study treatment should NOT be considered withdrawn from the study. These subjects should have all Week 260 protocol assessments performed approximately four weeks after their last dose of secukinumab and then enter the treatment-free follow-up period (Weeks 264 and 268). Subsequently, these subjects should enter the follow-up 2 period. On the EOT eCRF (Week 260), the site staff must record the date and primary reason for stopping study treatment.

The investigator must contact the IRT when the subject completes the assessments on Week 260 due to study treatment discontinuation.

Study treatment must be discontinued after emergency unblinding.

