5.5.12 Early study termination

The study can be terminated at any time for any reason by Novartis. Should this be necessary, the patient should be seen as soon as possible and properly managed for a prematurely withdrawn patient. The investigator may be informed of additional procedures to be followed in order to ensure that adequate consideration is given to the protection of the patient's interests. The investigator will be responsible for informing IRBs and/or ECs of the early termination of the trial.

6 Visit schedule and assessments

[Table 6-1](#) Assessment Schedule lists all of the assessments and indicates with an "x" when the visits are performed.

Subjects should be seen for all visits on the designated day within the allowed “visit window” specified below or as close to it as possible.

During the treatment period, subjects may be seen at an unscheduled visit, e.g. if they experience deterioration of psoriasis, or AEs that in the opinion of the investigator need intervention or repeated laboratory testing. During these unscheduled visits, study treatment will NOT be administered. A visit window of “±5” will be allowed for Week 52 to Week 260 during the treatment period during the follow-up period or as close to it as possible.

Subjects who discontinue study treatment will continue to be followed for safety assessments. They are not considered withdrawn from the study.

Subjects who discontinue study treatment before completing the study, and those who prematurely withdraw from the study for any reason should be scheduled for a study visit 4 weeks after their last study treatment administration, at which time all the assessments listed for EOT (Week 260) will be performed (see [Section 5.5.10](#)). Subjects will return to the study site for further assessments as indicated under the follow-up visits (Weeks 264 and 268) (see [Section 3.1](#)).

Only subjects who prematurely discontinued study treatment should enter follow-up 2 period after completion of follow-up visits (Weeks 264 and 268). Follow-up 2 period includes telephone calls every 3 months until 4 years from the time subjects have been enrolled into CAIN457A2304E1 as well as potential unplanned assessments e.g physical examinations, vital signs and laboratory assessments during this time.

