6.5.6 Pregnancy and assessments of fertility

A serum β -hCG test will have already been performed on all women of child-bearing potential who entered studies CAIN457A2304 and CAIN457A2307.

All women of child-bearing potential who are eligible to participate in this extension study will have a local urine pregnancy test as indicated in [Table 6-1](#). If positive, they will undergo a serum pregnancy evaluation conducted at the Central Laboratory

Any woman whose resulting pregnancy test is positive (based on serum β -hCG as defined by the Central Laboratory) at the Enrollment Visit Week 52 will have to discontinue from this extension study and return to the follow-up assessments in the core study.

A positive urine pregnancy test during the treatment periods of the study requires immediate interruption of study treatment until serum β -hCG is performed and found to be negative. If the serum β -hCG test is positive, the subject must be discontinued from the trial (as per [Section 5.5.10](#))

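### After a positive serum pregnancy test, Protocol 5.5.5 and 6.5.6 discontinue the subject from the trial, while 5.5.9 stops treatment only and keeps her in follow-up 2; the passages need one disposition

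*Protocol*

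**What the plan says.** Protocol 5.5.5 (dose adjustments and interruptions) requires treatment to be interrupted on a positive urine test until a serum test is negative. If the serum test is positive, "the subject must be discontinued from the trial". Section 6.5.6 (pregnancy and assessments of fertility) repeats this sentence and adds a cross-reference to 5.5.10.

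Protocol 5.5.9 lists pregnancy among the circumstances in which study treatment must be discontinued, and gives the consequence: "Subjects who discontinue study treatment should NOT be considered withdrawn from the study". Those subjects have the Week 260 assessments about four weeks after the last dose and then the Week 264 and 268 visits. It continues: "Subsequently, these subjects should enter the follow-up 2 period". No exception is made for pregnancy.

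The Amendment 2 rationale explains why follow-up 2 was added. Subjects who stopped treatment early were being evaluated for less than four years, and the regulator had asked for four. It states: "Evaluation of subjects should continue when achievable even if treatment is not continued for the duration".

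The glossary keeps the two ideas apart. Stopping study treatment permanently "may or may not also be the point/time of premature patient withdrawal".

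**The concern.** The same event leads to two dispositions. Under 5.5.9 the subject stays in the study and is telephoned every three months until four years after enrolment. Under 5.5.5 and 6.5.6, read as written, she leaves the trial.

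Three things in the protocol depend on which reading a site adopts:

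- **Length of evaluation.** Follow-up 2 exists to complete the four-year evaluation of subjects who stop treatment early.
- **SAE reporting (7.2).** For subjects who enter follow-up 2, every SAE is reportable until the last telephone contact. For others the window closes 12 weeks after the last dose or 30 days after the end of participation, and later SAEs are reported only if the investigator suspects a causal relationship.
- **Disposition and database lock (3.5).** Completing follow-up 2 after stopping treatment and withdrawing from the study are separate routes to completion, so the same event could be classified differently at different sites.

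**Working it through.** The plan gives no figure to reproduce. The check is a comparison of the passages, followed by simple arithmetic on the time at stake.

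**Step 1: is the difference only loose wording?**

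- The glossary separates treatment discontinuation from withdrawal, so the two phrases are not synonyms.
- Section 6.5.6 also covers a positive test at the Week 52 enrolment visit. That woman discontinues from the extension and returns to core-study follow-up, so there the phrase does mean leaving the study. A site could read the next paragraph of 6.5.6 the same way.
- The Amendment 2 change list names 3.1, 3.5, 5.5.9, 5.5.10, 6, 7.2 and 9.5.2, among others, but not 5.5.5 or 6.5.6. It also mentions unnamed minor changes, so this suggests, without proving, that the two sections were not aligned.

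**Step 2: does the cross-reference settle it?**

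Section 6.5.6 points to 5.5.10, the emergency code break. Taken literally, 5.5.10 discontinues subjects from study treatment and sends them to Week 260, two follow-up visits and follow-up 2. If the pointer is a stale reference to the discontinuation rules, it leads to 5.5.9, with the same result. Either way it points towards follow-up 2, which does not fit the words *from the trial* in the same sentence. Section 5.5.5 has no cross-reference.

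**Step 3: time at stake per subject.**

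Inputs:

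- Enrolment is at Week 52 (3.1).
- Follow-up 2 ends four years after enrolment (3.1): 52 + 208 = Week 260. With 365.25-day years it is 52 + 4 × 365.25 / 7 = Week 260.7.
- Minimum safety contact runs to 12 weeks after the last dose (section 6).
- Calls are every three months (3.1): 365.25 / 4 / 7 = 13.04 weeks apart.

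Assumption: a subject discontinued from the trial is contacted only to that 12-week minimum.

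Formula: weeks at stake = 260 − (week of last dose + 12). Calls = weeks at stake / 13.04, rounded down.

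| Last dose | Calculation | Weeks at stake | Calls |
|---|---|---|---|
| Week 52 | 260 − 64 | 196 | 15 |
| Week 104 | 260 − 116 | 144 | 11 |
| Week 156 | 260 − 168 | 92 | 7 |
| Week 208 | 260 − 220 | 40 | 3 |
| Week 248 | 260 − 260 | 0 | 0 |

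Using Week 260.7 adds 0.7 week to each row. If contact ended at the end-of-treatment visit, four weeks after the last dose, the first four rows would each rise by 12 − 4 = 8 weeks, to 204, 152, 100 and 48.

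**Step 4: number of subjects.**

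This would need the share of women, the share of child-bearing potential and a pregnancy rate. The documents give none of these, so no count is offered.

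**The case against.** The strongest reply is that the documents already lead to follow-up 2. Amendment 2 speaks of all subjects who stop treatment early and makes no exception for pregnancy. Section 6 ties entry to follow-up 2 to treatment discontinuation and completion of the Week 264 and 268 visits. The description of withdrawal in 5.5.9 covers stated intention, failure to return and loss to follow-up, and does not include pregnancy. The pointer in 6.5.6 leads the same way. This narrows the conflict to the words *from the trial* in both sections and to 5.5.5, which stands alone. It does not remove it, because a site acting on 5.5.5 finds nothing there that sends it on to 5.5.9.

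The reply also limits the consequences, and these limits stand. A reader might infer three stronger things that the documents do not support:

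- *That all study assessments end.* Section 6 schedules subjects who withdraw for any reason for the end-of-treatment assessments, has them return for the Week 264 and 268 visits, and requires safety contact to 12 weeks after the last dose. Section 5.5.9 also asks withdrawing subjects to return. What is exposed is mainly follow-up 2.
- *That the pregnancy itself goes unobserved.* Section 7.4 requires a pregnancy occurring on study treatment to be reported within 24 hours and followed to its outcome, separately from the visit schedule. What is exposed is the other adverse event, SAE and concomitant medication follow-up.
- *That the safety summaries would be biased.* Protocol 9.5.2 puts follow-up 2 data into listings unless the event is treatment emergent. That window closes at 84 days, which is the same 12 weeks. SAP 1.9.1 likewise summarizes only treatment-emergent events and lists follow-up 2 separately.

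**Conclusion.** The contradiction is in the current text and affects conduct. Sections 5.5.5 and 6.5.6 can be read as ending participation where 5.5.9 ends only treatment. For a subject handled under the first reading, roughly 40 to 196 weeks of four-year evaluation are at stake for last doses from Week 208 back to Week 52, falling to none from about Week 248. The extended SAE reporting window is at stake with it.

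These figures assume that contact stops at the 12-week minimum. They are per subject, and no total can be derived from the documents. The effect falls on the four-year post-marketing evaluation, and the planned summary tables would barely change. The point is worth correcting because it touches a stated regulatory commitment. It does not threaten the primary safety analysis.

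**What to change.** Reconcile 5.5.5, 6.5.6 and 5.5.9 so that a positive serum test during treatment has one disposition, and check that disposition against the four-year evaluation in Amendment 2. State explicitly whether the Week 260, 264 and 268 assessments and follow-up 2 apply, and use the glossary's terms for stopping treatment and for leaving the study. Correct the cross-reference in 6.5.6. Section 6 uses the same 5.5.10 pointer for early discontinuation and should be checked at the same time. Which disposition is clinically right is for the sponsor to decide.

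The cost is wording in up to three sections and one or two cross-references, made in a protocol amendment with the approvals that section 11.1 requires. Both the follow-up visits and follow-up 2 already exist, so no new procedure has to be designed.
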